Desmoid tumor represents a heterogeneous disease and can have an unpredictable clinical course, particular related to growth rate (De, I et al., 2000; de et al., 2009). Often, the slow growth and slow response of desmoid tumor precludes the use of previously established standardized radiographic measurements of response, such as the Response Evaluation Criteria in Solid Tumors (RECIST). This is particularly true in shorter treatment schedules such as the one proposed in this pilot study. Therefore, other surrogate markers of response are needed.

Burris and colleagues were one of the first groups to look at pain as a measure of 'clinical benefit' within the context of a therapeutic cancer study (Burris, III et al., 1997). Clinical benefit was a composite assessment of pain, performance status, and weight. Clinical benefit was measured prospectively as a primary endpoint of the study. Patients with advanced pancreatic cancer were randomized to receive gemcitabine or 5-fluorouracil (5-FU). The designation for pain integrated both the subjective report of pain intensity as well as analgesic consumption.

Pain intensity was measured daily on the Memorial Pain Assessment Card (MPAC) 0-100 visual analog scale, and a positive response was associated with an improvement of $\geq 50\%$ from baseline sustained for ≥ 4 weeks. Analgesic consumption was measured weekly in morphine-equivalent milligrams, and a positive response was indicated by a decrease of $\geq 50\%$ from baseline, sustained for ≥ 4 weeks). Clinical benefit was experienced by 24% of gemcitabine-treated patients compared with 5% of 5-FU treated patients.

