Recently, Ohorodnyk and co-authors performed a literature search for reports of all clinical trials (phase I, II, and III) published in the Journal of Clinical Oncology from 1997-2008 citing 'clinical benefit' (Ohorodnyk et al., 2009). Eligible trials were those reporting clinical benefit as an endpoint. Clinical benefit was classified as patient-centered if it referred to improvement in the clinical parameters used by Burris and colleagues or in other disease-related symptoms. 71 trials reporting clinical benefit were identified: 37 in breast, 8 in pancreas and 26 in other cancers. Among the 71 trials reporting clinical benefit, 31 (44%) trials had that endpoint defined as a primary or secondary study objective. Of note, the authors found a steady increase in the number of trials using clinical benefit as an endpoint; in the second half of the study period the number of trials increased from 17 to 54.

The locally invasive nature of desmoid tumor frequently results in significant pain (Hosalkar et al., 2006). Improvement in pain for patients undergoing treatment for desmoid tumor has been described in a few previous studies. Constantinidou et al demonstrated improvement in pain with the use of pegylated liposome doxorubicin (PLD) (Constantinidou et al., 2009). Eleven of 12 patients with desmoid tumor treated with PLD had clinical benefit in terms of pain relief or improved mobility and cosmesis. Skubitz and colleagues noted improved pain in a sunitinib-treated patient with recurrent desmoid tumor (Skubitz et al., 2009). The pain improved and resolved by 28 days of treatment. A reduction in tumor size was noted after 5 months of therapy. Neither study mentioned the specific pain assessment tool utilized.

To our knowledge, no pediatric study has used pain as a primary or secondary endpoint in cancer treatment. Because of pain often associated with desmoid tumor and the slow changes in tumor size, we will use pain assessment as a surrogate marker of response in this study. Validated pain assessment scales, depending on the age of the patient, have been established for our patient population (Bijur et al., 2003; Hain, 1997; von Baejer, 2006). For this pilot study, the Wong-Baker FACES scale will be used for patients ≥ 3 and < 10 years of age and the numeric scale will be used for patients who are 10 years of age or older.

Summary of trial design

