H and E staining will be used to verify that the arrayed tissue/slides contain desmoid-type fibromatosis. To assess mTOR pathway activation, immunohistochemical staining will be conducted for the following proteins and phosphoproteins: p-p70S6K, p-4E-BP1, both of which represent targets of mTOR; and p-AKT as this pathway could be activated as a drug resistance mechanism (see Figure 1). Staining will be performed on the (a) post-treatment specimens, (b) paired, pre-treatment, archived specimens (if available), and (c) archived non-chemotherapy-treated specimens from the UCLA tumor bank (approximately 50 are available). All samples will be anonymized using an alpha-numeric code, with the key maintained in a HIPAA-compliant, secure database or locked file on the UCLA Server.

Routine histology protocols (including positive and negative controls) will be used. Quantitative analysis will be accomplished utilizing an Immuno-Reactive Score (IRS) as previously described (Noske et al., 2008; Chen et al., 2009; Lin et al., 2006). Specifically, the percentage of positive cells will be scored as: 0 (0%); 1 (<10%); 2 (11-50%); 3 (51-80%); 4(>80%). The staining intensity will be scored as: 0 (negative), 1 (weak), 2 (moderate), and 3 (strong). To derive the IRS, the percentage of positive cells and staining intensity will be multiplied together, resulting in a value from 0 to 12. IRS values 0 to 3 will be considered negative and values of 4 to 12 will be considered positive. Of note, samples will be scored by an experienced pathologist, blinded to whether the samples represent pre- or post-treatment or archived non-chemotherapy treated specimens.

Pain Assessment

Validated pain assessment measures, using the numeric and Wong-Baker FACES scales, will be collected at specific study time points. Patients ≥ 3 and < 10 years of age will use the Wong-Baker FACES scale and patients who are ≥ 10 years of age will use the numeric scale. A positive response will be associated with an improvement of $\geq 50\%$ from baseline after 4 weeks. A negative response will be associated with any worsening from baseline after 4 weeks. A stable response will be any other result.

Radiographic Assessment

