
proportion positive compared between the two groups using Fisher's exact test. Finally, pre- and post-treatment values within patients enrolled on the trial will be compared using paired t or Wilcoxon, signed-rank tests.

Secondary Objectives

These scientific endpoints will be mostly exploratory, given the small numbers of patients enrolling in this pilot study. Nonetheless, we anticipate finding that 4 weeks of sirolimus will result in decreased tumor-associated pain. Pain assessments will be made using validated age-based pain assessment scales and compared pre- and post-treatment using a paired t test. Descriptively, the number of patients showing >50% improvement in their pain score, worsening pain, or between 0 and 50% improvement will be tabulated. Having decreased pain in approximately 60% of patients without substantial toxicity will be viewed as a success.

Patients will also be followed for recurrence post-surgery. As a benchmark, in a similar cohort of patients treated on the Pediatric Oncology Group 9650 study with vinblastine and methotrexate, the progression-free survival rate at 1 year was 58%. Vinblastine and methotrexate, which most would agree represents the current standard of care for desmoid tumor that is not amenable to surgery or radiation, is associated with significant toxicity: 18 of 27 (66%) patients on that trial experienced NCI grade 3 or 4 toxicity. Having histochemical evidence for decreased mTOR pathway activation with less toxicity will be viewed as a success, and lead the investigators to explore ways to test sirolimus in a randomized, phase II study in which the drug is used for patients with unresected disease and for patients in which the drug is continued following surgical resection of disease.

An independent statistician has been recruited from Center for Outcomes Research and Evaluation (CORE) at Maine Medical Center Research Institute. [name], assisted in the original presentation of this project. There will be no interim analysis performed; analysis will be performed at study completion. If [name] is not available, [name]. Senior Biostatistician at CORE, will be the lead statistician for this project. [name] will be assuming the analysis or consulting on this project as this is her area of expertise and her background is in translational research.

Early Stopping Rules

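### Pain response is defined and analysed on the pain score alone, so changes in analgesic use over the four weeks can misclassify patients in either direction

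*Combined protocol and SAP*

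**What the plan says.** The background section on pain as a surrogate marker gives pain an important role: "we will use pain assessment as a surrogate marker of response in this study". It first describes a randomized pancreatic cancer trial, of which it says: "The designation for pain integrated both the subjective report of pain intensity as well as analgesic consumption". On the second component it reports: "Analgesic consumption was measured weekly in morphine-equivalent milligrams, and a positive response was indicated by a decrease of" at least 50%, sustained for four weeks or more.

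This trial's own definition is under Pain Assessment. "A positive response will be associated with an improvement of" at least 50% on the age-appropriate scale after 4 weeks. At the other end, "A negative response will be associated with any worsening from baseline after 4 weeks". Everything else is stable. Analgesics are not mentioned.

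Statistical Analysis, Secondary Objectives, analyses the same score: "Pain assessments will be made using validated age-based pain assessment scales and compared pre- and post-treatment using a paired t test". It adds a count: "Descriptively, the number of patients showing >50% improvement in their pain score, worsening pain, or between 0 and 50% improvement will be tabulated". It then sets a criterion: "Having decreased pain in approximately 60% of patients without substantial toxicity will be viewed as a success".

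The Required Observations table makes the weekly pain scale mandatory but has no row for analgesics or concomitant medication. The eligibility criteria restrict drugs that affect sirolimus metabolism and do not ask for stable analgesics.

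**The concern.** A pain score reflects both the disease and the pain medicine taken on the day. The protocol itself notes that desmoid tumors are often painful, so analgesic use in this population is foreseeable, and it may change during the four weeks before surgery. All 15 patients receive sirolimus. The archived controls are tissue specimens and supply no pain data. Nothing in the design therefore separates a score that changed with sirolimus from one that changed with analgesics.

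The stated rule, followed exactly, can misclassify in two ways:

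- A patient whose score falls by half or more after an analgesic increase is a positive response.
- A patient who needs less analgesia at an unchanged score is stable, although that may be real benefit.

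At stake is the reading of the first secondary objective and of the 60% criterion. The protocol also gives symptomatic improvement as an example of a reason why a physician might continue sirolimus after surgery, outside the trial.

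**Working it through.** The plan states no sample size, power or significance level for pain, so there is no planned figure to reproduce. The check has a textual part and an illustrative part.

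**Text, side by side**

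| Item | Earlier trial, as described | This trial |
|---|---|---|
| Pain intensity | at least 50% improvement, sustained 4 weeks or more | at least 50% improvement, after 4 weeks |
| Analgesic consumption | weekly, morphine equivalents, at least 50% decrease | not in any definition or analysis |
| Comparator for pain | randomized | none |

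**Weight of one patient.** From the documents, n = 15 and the criterion is about 60%, so 0.60 × 15 = 9 patients. One patient is 1/15 = 6.7 points. Suppose k of nine improvers had increased analgesics (k is an assumption). The rate is then (9 − k)/15:

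- k = 0: 9/15 = 60% (exact 95% CI 32.3 to 83.7%)
- k = 1: 8/15 = 53%
- k = 2: 7/15 = 47% (21.3 to 73.4%)
- k = 3: 6/15 = 40% (16.3 to 67.7%)

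**Chance of reaching 9 of 15, upward error.** Let p be the share with relief due to sirolimus, and q the share of the others who improve only because analgesics were increased. Both are assumed. The observed rate is π = p + (1 − p)q, and the chance is P(X ≥ 9) with X binomial(15, π). For example, p = 0.40 and q = 0.2 give π = 0.40 + 0.60 × 0.2 = 0.52 and a chance of 36%.

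| p | q = 0 | q = 0.1 | q = 0.2 | q = 0.3 |
|---|---|---|---|---|
| 0.30 | 1.5% | 6% | 16% | 33% |
| 0.40 | 9.5% | 20% | 36% | 55% |
| 0.50 | 30% | 45% | 61% | 76% |

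**Downward error, same formula.** Let a share r of true responders take their benefit as less analgesia at an unchanged score, so π = p(1 − r). With p = 0.60 and r = 0 the chance of 9 or more is 61%. With r = 1/6, π = 0.60 × 5/6 = 0.50 and the chance is 30%. With r = 1/3, π = 0.60 × 2/3 = 0.40 and the chance is 9.5%. Here p and r are assumed.

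**Paired t test.** Simulation used n = 15, two-sided 0.05 and 40,000 runs. It assumed no drug effect, an SD of other change of 2 points, and a 3-point fall in a share q with increased analgesics. The chance of a significant improvement is 2.5% (q = 0), 6% (0.1), 14% (0.2) and 25% (0.3).

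These figures show how sensitive the result is. They do not predict how often analgesics will change, since the documents give no frequency.

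**The case against.** Much of the case on the other side stands.

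- **Precedent, not model.** A reader might infer that the protocol adopted the earlier endpoint and copied it incompletely. It does not say so. It describes that trial as an early example, uses the same 50% cut, and also leaves out the weight and performance-status components, daily scoring and the sustained-response requirement. The comparison shows only that the authors knew analgesic use could belong in a pain measure.
- **Direction.** It is tempting to say the bias favours success. The documents do not support that: both errors are possible and neither frequency is given.
- **Data collection.** One cannot say that analgesic use goes unrecorded. Case report forms are cited but not included, and a weekly history is scheduled. What can be shown is that no definition or analysis uses such data.
- **Denominator.** Pain at entry is not an eligibility requirement, so fewer than 15 patients may be evaluable. The criterion is also approximate and tied to the absence of substantial toxicity.
- **Analgesics for other reasons.** The toxicity table lists arthralgia, myalgia, abdominal and chest pain, and stomatitis. An analgesic started for one of these should not cancel a tumour-pain response, so indication must be recorded.
- **Importance.** The endpoint is mostly exploratory, and the step to a randomized study is tied to histochemical evidence with less toxicity, not to pain.

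None of this removes the gap. The score alone still misclassifies, and neither the exploratory label nor more patients would correct that.

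**Conclusion.** The point holds as a cheap improvement to a secondary, mostly exploratory endpoint. Pain response, the paired t test, the tabulation and the 60% criterion all ignore analgesic use, in a single-arm period with nothing to absorb changes in it. An analgesic increase does not by itself make a patient a responder; the score must also fall by at least 50%. But such a patient can count, and a patient with the same score on less medicine gets no credit.

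The arithmetic is firm on one thing: with 15 evaluable patients, each reclassification moves the rate by 6.7 points. The move from 60% to 47% or 40% assumes that two or three of nine improvers had increased analgesics, and the probabilities above rest on assumed p, q, r, SD and score fall. The net direction is unknown. The primary endpoint and its power statement are not affected.

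**What to change.** 1. **Data.** At baseline and at each required weekly pain assessment, record current analgesics, their indication (tumour pain or other), and whether use for tumour pain is increased, the same or decreased from baseline. State in advance how as-needed use and drug switches are coded.
2. **Pain Assessment section.** Count a positive response only if analgesics for tumour pain are not increased at week 4. A patient whose score halves after an increase then falls into the existing stable category.
3. **Secondary Objectives.** Apply the same condition to decreased pain in the 60% criterion. Tabulate score change by analgesic change, so that patients who needed less medicine are also visible. Repeat the paired t test without patients whose analgesics for tumour pain were increased. Label it a sensitivity analysis, because it selects on something that happens after baseline.
4. **Reporting.** Give the score-only result alongside.

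This is a rule for recording and analysis and places no restriction on pain treatment. It costs a few extra items at a visit that already takes place, one extra table, and possibly a lower stated response rate. It does not remove placebo response or regression to the mean, so it would not isolate a sirolimus effect. Changes in analgesic use may be hard to reconstruct later, so the record should be specified prospectively.
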